Participants will be asked to respond to structured questionnaires through face-to-face interviews conducted by trained interviewers using computer tablets prior to the launch of the intervention, after completing the intervention sessions and at the end of the study period. Data to be collected include: basic demographic information (e.g. sex, age, education level, relationship status (e.g. married, partnered, single), living arrangements (whether they live with a parent or guardian, how many people are in their household, and relationship to those people), as well as contact information (phone number, place of residence); HIVrelated information including how long since diagnosis, current ART regimen, last CD4 and viral load test date and results, disclosure status, self-reported adherence; social support measures covering emotional, instrumental, informational and network social support dimensions; factors associated with poor retention and adherence, including depression/anxiety, alcohol and other substance use, and perceived and experienced stigma; and access to and use of mobile telephones and social media applications. Forms will be administered at baseline and again at six months and endline, which will be 6 and 12 months after the intervention is initiated, respectively. Six-month and endline questionnaires will include additional, closedand open-ended questions pertaining to intervention participation. Telephone interviews may be conducted in place of face-to-face interviews for participants who, after at least 2 attempts to schedule in-person interviews, are unable or unwilling to return to the clinic for interviews after the intervention and at the end of the study period.

Clinical data

A data abstraction sheet will be developed to abstract relevant clinical data for each study participant. Trained data collectors will abstract data periodically (approximately quarterly) through 15 months after enrollment. As noted, the form will only record the participant's unique study ID for identification purposes. Data to be abstracted will include: date and results of CD4 cell counts and viral load tests; date of HIV diagnosis; date of ART initiation; WHO clinical stage at ART initiation; dates of ART refills; dates of ART clinic visits.

Participation data

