For this study, we will be implementing the full version of the online support group intervention piloted in the feasibility study and conduct a randomized controlled trial to evaluate its impact on retention in HIV care services. The intervention components include:

- Informational messages that reflect the content of the structured group counseling curriculum, • Positive Connections, and are posted to the group wall on a regular basis several times a week, for approximately 4 to 4.5 months
- Moderated, closed group chats in a "secret" Facebook group where YLHIV can interact with their peers and with a trained health counselor
- Access to a trained counselor via Facebook Messenger or phone for the duration of the intervention who will be able to provide information or basic counseling on ART/HIV care related issues, with referral to health care services as needed

Ι. Study Aim and Objectives

The principle aim of this research is to gather evidence on an intervention designed to improve retention in HIV care services among youth living with HIV, ages 15-24 years, enrolled in ART services.

The objectives of the study are:

- 1. To test the effectiveness of a structured online support group (SMART Connections) to increase retention in HIV services among YLHIV.
- 2. To examine the effect of the SMART Connections on secondary outcomes of social support, HIV knowledge and treatment literacy, and ART adherence among YLHIV.
- 3. To test the potential mediating effect of social support on the relationship between the intervention and primary outcome.
- 4. To document the costs of the intervention and calculate the unit cost per YLHIV retained. Intervention costs will also be descriptively compared to the costs of adolescent-focused, in-person support groups in the region.
- 5. To document participant engagement and perspectives regarding the content and delivery of the intervention to inform scalability and sustainability.
- 6. To document implementation and health care provider and support group facilitator perspectives regarding intervention content and delivery to inform scalability and sustainability.

The study's primary outcome is retention in HIV services at 6-9 months after enrollment. The study's secondary outcomes are:

- 1. ART adherence
- 2. Social support

3. HIV knowledge and treatment literacy

11. Study Design

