Randomization groups will be concealed in sequentially numbered, sealed opaque envelopes (SNOSE). We will instruct study staff never to open an envelope until the participant has given consent to participate in the study, is found to be eligible for the study, and is available to start intervention and control study procedures. The opened randomization envelopes will be retained as source documents and will be kept under secure and restricted access to protect the confidentiality of the participants.

This is an open-label study – neither study staff nor participants will be blinded to study treatment arms after the point of randomization. Nonetheless, strict policies will be in place to preserve randomization integrity. Randomization documentation will be stored in a secure location. Data recording, assessment of the primary and secondary study outcomes, and other assessments will be blinded to treatment arm where possible.

IV. General Analytic Considerations

All primary analyses will be conducted under the intent-to-treat (ITT) principle, whereby participant data will be analyzed in the group each participant is randomized to regardless of randomization errors or other protocol violations. A per protocol analysis will be conducted if more than 5% of the population is affected by protocol violations such as randomization errors.

A. Data Sources

1. Structured questionnaires

Topics: Demographic information; HIV-related information; social support measures;

depression/anxiety, alcohol and other substance use, and perceived and experienced stigma; and access to and use of mobile telephones and social media applications. Sixmonth and endline questionnaires will include additional questions pertaining to intervention participation.

Timing: Baseline, endline

Source: Structured interview

Format: Face-to-face interview with data entered on a mobile tablet Population: Intervention participants

2. Clinical data abstraction

Topics: Date and results of CD4 cell counts and viral load tests; date of HIV diagnosis; date of ART initiation; WHO clinical stage at ART initiation; regimen substitutions and switches;

treatment discontinuation and interruptions; dates of ART refills; dates of ART clinic visits. Timing: Periodically, through 12 months after enrollment.

Source: Electronic medical record system at participating health clinics Format: Electronic form captured on mobile tablet

Population: Intervention participants

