For the survival analysis, we will create two sets of variables indicating retention using a 28 day cutoff and using a 90 day cutoff to reflect the fact that the national guidelines for retention in HIV services changed from 12 weeks (i.e. 90 days) to 4 weeks (i.e. 28 days). For each recorded visit, we will also assess whether the participant is within their scheduled window and the number of days between the scheduled visit date and the date the visit was actually attended (v1 denotes the first attended visit after study enrollment; v2, v3, v4, etc. will be calculated for all visits between study enrollment and date of EL questionnaire (or date EL questionnaire should have been conducted, based on enrollment date, for those LTFU in the study at endline):

For each visit, starting at visit 2 (i.e. v2):

- v2_days_aftersched = [visit date (v2q036)] [date of prior scheduled visit (v1q044)]; missing if either date is . or jan 1 1990
- v2_ltfu_28 = 1 if v1_days_aftersched >28; = 0 if v1_days_aftersched ≤28; missing if next scheduled visit date (v1q044) is missing (. or jan 1 1990).
- v2_ltfu_90 = 1 if v1_days_aftersched >90; = 0 if v1_days_aftersched ≤90; missing if next scheduled visit date is missing (. Or jan 1 1990).

1tfu 28 LTFU status for survival analysis using 28 day cutoff

- **ltfu_28**=1; lost to follow-up
 - o v2 ltfu 28==1 OR v3 ltfu 28==1 OR v4 ltfu 28==1, etc.
 - o Appears retained for all recorded visits, but earliest value of today_el, today_el_approx, latest_mre falls MORE than 28 days after latest instance of vnq044
- ltfu 28=0; retained

- o v2 ltfu 28==0 AND v3 ltfu 28==0 AND v4 ltfu 28==0, etc. AND the earliest value of today el, today el approx, latest mre falls within 28 days of latest instance of **vnq044**
- 1tfu 28=8; transferred out
 - o Retained up to the date of transfer (transfer==1 and q027, transfer date, must be non-missing)
- **ltfu 28**=9; died
 - o Retained up to the date of death (death==1 and q028, death date, must be non-missing)

1tfu 90 LTFU status for survival analysis using 90 day cutoff

- **ltfu 90**=1; lost to follow-up
 - o v2 ltfu 90==1 OR v3 ltfu 90==1 OR v4 ltfu 90==1, etc.
 - o Appears retained for all recorded visits, but earliest value of today el, today el approx, latest mre falls MORE than 90 days after latest instance of **vnq044**

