- ltfu 90=0; retained ٠ o v2 ltfu 90==0 AND v3 ltfu 90==0 AND v4 ltfu 90==0, etc. AND the earliest value of today el, today el approx, latest mre falls within 90 days of latest instance of **vnq044**
- ltfu 90=8; transferred out ٠
 - o Retained up to the date of transfer (transfer==1 and q027, transfer date, must be non-missing)
 - **ltfu 90**=9; died o Retained up to the date of death (death==1 and q028, death date, must be non-missing)

ret time 28 Time in days retained until LTFU, transfer, death, or censor

- If 1tfu 28=0
 - o ret time 28==[latest follow-up date i.e. v8q044] [BL survey date, today bl] IF v8q044<today el/today el approx</pre>
 - o ret time 28=[latest visit date i.e. v7q036]+28-today bl IF retained for all visits recorded and latest available follow-up date is missing
 - o ret time 28=[today el/today el approx]-today bl IF latest follow-up date >today el/today el approx OR latest visit date +28 >today el/today el approx
- If **1tfu 28**=1
 - o ret time 28=[latest follow-up date prior to LTFU, i.e. v6q044] -[today bl]
 - o ret_time_28=latest visit date prior to LTFU, i.e. v5q036 + 28 today bl IF latest follow-up date prior to LTFU is missing
- if **1tfu 28**=8
 - o ret time 28=latest follow-up date prior to or after transfertoday bl IF q027>today bl AND q027≤latest follow-up date prior to transfer
 - o ret time 28=latest visit date prior to transfer + 28 -today bl IF q027>today bl AND latest follow-up date prior to transfer is missing
- if **1tfu 28=9**
 - o ret_time_28=q028-today_bl

ret time 90 Time in days retained until LTFU, transfer, death, or censor

- If **ltfu 90=0**
 - o ret_time_90==[latest follow-up date i.e. v8q044] [BL survey date, today_b1] IF v8q044<today el/today el approx</pre>
 - o ret_time_90=[latest visit date i.e. v7q036]+28-today_b1 IF retained
 for all visits recorded and latest available follow-up date is
 missing
 - o ret_time_90=[today_el/today_el_approx]-today_bl IF latest follow-up
 date >today_el/today_el_approx OR latest visit date +28
 >today_el/today_el_approx
- If **ltfu_90**=1
 - o ret_time_90=[latest follow-up date prior to LTFU, i.e. v6q044] [today_b1]
 - o ret_time_90=latest visit date prior to LTFU, i.e. v5q036 + 28 today_bl IF latest follow-up date prior to LTFU is missing
- if **ltfu_90**=8
 - o ret_time_90=latest follow-up date prior to or after transfertoday_bl IF q027>today_bl AND q027≤latest follow-up date prior to transfer
 - o ret_time_90=latest visit date prior to transfer + 28 -today_bl IF

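### The SAP's survival variables cannot normally record a loss in the last 28 (90) days before endline and leave the first interval after enrolment unsettled, so Kaplan-Meier retention reads too high in both arms when endlines fall at 6-9 months

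*SAP*

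**What the plan says.** All of this is in SAP section IV.C, under the heading on retention for survival analysis, unless stated otherwise.

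**End of follow-up.** Visit variables "will be calculated for all visits between study enrollment and date of EL questionnaire". When the last scheduled visit has no attendance, loss is coded only under this condition: "Appears retained for all recorded visits, but earliest value of today_el, today_el_approx, latest_mre falls MORE than 28 days after latest instance of vnq044". The retained code is the mirror image: "the earliest value of today el, today el approx, latest mre falls within 28 days of latest instance of" the last scheduled date. Time for a retained participant whose last scheduled date is before endline stops at that date ("ret time 28==[latest follow-up date i.e. v8q044] [BL survey date, today bl"; the minus sign is lost in the text). If the next scheduled date lies beyond endline, time runs to endline ("ret time 28=[today el/today el approx]-today bl IF latest follow-up date" is after endline). The 90-day variables follow the same pattern.

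**Timing.** SAP section I: "The study's primary outcome is retention in HIV services at 6-9 months after enrollment". Section VI, Objective 1, stops the analysis at day 270. Record abstraction runs beyond that. SAP IV.A: "Timing: Periodically, through 12 months after enrollment". Protocol, Clinical data: "Trained data collectors will abstract data periodically (approximately quarterly) through 15 months after enrollment".

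**First interval.** `v1` is the first visit attended after enrolment, and lateness is scored from visit 2 onward. A participant with no visit in the study period gets missing time and status, and section IV.B makes the primary analyses complete-case. On the other side, the `n_visits` code allows `v1` before baseline, section VI keeps participants with zero survival time, and section IV states intention to treat.

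**Visit-2 flags.** `v2_ltfu_28` and `v2_ltfu_90` are built from `v1_days_aftersched`. The SAP defines only `v2_days_aftersched`.

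**The concern.** Having no event yet is not itself an error; a participant 10 days overdue is not yet lost under a 28-day rule. The fault is that the censoring time depends on non-attendance. Of two participants under observation to the same endline, the one who missed the last visit leaves the risk set at the missed date and the one who attended stays in it to endline. The estimated hazard is zero by construction over each participant's last 28 (90) days, so the curve is flat there. Later records that could show whether the visit was eventually made are set aside.

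Kaplan-Meier retention by arm is a stated primary result, so its level matters. The absolute difference between arms also shrinks and events are lost.

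The first-interval conflict decides who enters the primary analysis. Read literally, a late first return is never tested, and someone who never returns is dropped instead of counted as lost. The protocol's background data show why this matters: 49% of those lost in the programme never came back after the initial ART visit. Nor can the effect be assumed equal by arm, because control participants receive the study phone at their next clinic visit and intervention participants at the group meeting (protocol, Intervention Description).

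**Working it through.** **Inputs** (SAP section III): 250 per arm; 12-month retention 0.45 and 0.575; exponential times; 80% power; two-sided 5%; 10% loss. Horizon: day 270 (SAP VI).

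**The plan's own figure.** HR = ln 0.575 / ln 0.45 = 0.693. Events needed = 4(1.960 + 0.842)² / (ln 0.693)² = 234. With exponential dropout of 10% at 12 months the mean event probability is 0.4655, so 234 / 0.4655 / 2 is about 251 per arm, against 250 stated. The sample size reproduces and is not in question.

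**Hazards per day.** Control: -ln(0.45)/365.25 = 0.002186. Intervention: -ln(0.575)/365.25 = 0.001515.

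**Effect of the last-window rule.** With a common endline E and no event datable in the last w days, Kaplan-Meier at min(E, 270) returns S(min(270, E-w)).

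| Rule | E | Control: true, reads | Intervention: true, reads |
|---|---|---|---|
| 28-day | 180 | 0.675, 0.717 | 0.761, 0.794 |
| 28-day | 240 | 0.592, 0.629 | 0.695, 0.725 |
| 28-day | 270 | 0.554, 0.589 | 0.664, 0.693 |
| 28-day | 298 or later | no effect | no effect |
| 90-day | 270 | 0.554, 0.675 | 0.664, 0.761 |
| 90-day | 360 or later | no effect | no effect |

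Example, control, 28-day, E = 270: exp(-0.002186 × 242) = 0.589 against exp(-0.002186 × 270) = 0.554.

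At E = 270 the true difference is 0.664 - 0.554 = 0.110. It reads 0.104 (28-day) or 0.087 (90-day). Events are 250 × (0.446 + 0.336) = 195 true, 250 × (0.411 + 0.307) = 179 under the 28-day rule and 141 under the 90-day rule. Power (Schoenfeld) = Φ(√events / 2 × 0.367 - 1.96): about 73% at 195 events and 69% at 179.

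**Simulation** (400,000 per arm, 30-day visits, random first due date). Levels sit above the closed form because loss is dated at the next due date.

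- E = 270, 28-day, control: true 0.574, SAP rule 0.611, the rule under Fix with records to day 365 0.574. For 90-day: 0.572, 0.698, 0.572.
- Endlines spread evenly over days 180-270 (an assumption), 28-day, read at day 240. Control: 0.612, 0.662, 0.612. Intervention: 0.711, 0.751, 0.711. The difference of 0.099 reads 0.089.

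**Hazard ratio.** At any day the share of the risk set inside its zero-hazard window depends only on the endline distribution. If that is the same in both arms, both hazards are scaled by the same factor, so under proportional hazards the ratio is not biased.

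**First interval.** If a share f has no post-enrolment visit and is dropped, true retention S reads S/(1-f). The documents do not give f. For assumed values of 2%, 5% and 10%, control 0.554 reads 0.565, 0.583 and 0.616. The SAP's `conservative` flag treats a first visit more than 56 days after baseline as a record gap. With a 30-day first due date, loss under the 28-day rule starts at day 30 + 28 = 58, so the flag marks nearly the same people. It is used only for descriptive tables.

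**The case against.** **Endline dates are not given.** The 6-9 months could describe when retention is assessed and not when interviews take place. The protocol places endline at 12 months, and the SAP still mentions 12-month retention. This stands as a condition on size. The SAP's own outcome window and 270-day cap nevertheless point to endlines early enough for the 28-day analysis to be affected.

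**Constant hazard may overstate the tail.** The protocol reports that two-thirds of programme losses occur in the first three months after initiation. If two-thirds of the planned 12-month loss fell by day 91 with a constant hazard afterwards, the day-270 28-day gap would drop from 3.5 to 1.8 points in control and from 2.9 to 1.4 in intervention, and the 90-day control gap from 12.1 to 6.0. This stands: the effect shrinks but stays. Enrolees may already have up to 12 months on ART, so their hazard shape is unknown.

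**The plan's 10% loss is left out of the event counts.** Including it gives about 189 falling to 174 events and power 71% falling to 68%, a similar decrement.

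**The test is largely intact, and the 28-day shift is smaller than the control arm's 95% half-width of about 6 points.** True, but a systematic shift is not covered by a confidence interval.

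**`ltfu_el` accepts visits up to 28 days after endline.** It does, but it does not feed the Kaplan-Meier variables.

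**There is one path to a loss inside the window.** If the final follow-up date is missing, an older date can trigger a loss timed at last visit plus 28 days. The missingness rules say to censor that case, so this is a further conflict.

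**The first-interval and variable-name points may be wording slips.** Possibly: keeping zero-time participants and allowing `v1` before baseline favour the benign reading. The text still has to say so.

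**Conclusion.** The concern holds. Under the SAP as written, a visit missed within 28 (90) days before the earlier of endline and last record extraction is normally censored at the missed date, while attenders run on. Retention is overstated in both arms whenever that point falls before day 298 (28-day) or day 360 (90-day). On the planning hazards with endline at day 270, the primary curves read about 3.5 points (control) and 2.9 points (intervention) too high, and the secondary 90-day curves 12.1 and 9.7 points too high. The cost to the primary test is about 16 events and 4 points of power. The last-window rule does not favour an arm under proportional hazards with like endline dates.

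These sizes rest on exponential times and on assumed endline dates; front-loaded losses would roughly halve them.

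The first-interval conflict is a contradiction to reconcile. Its size and its effect on the hazard ratio cannot be found from the documents. The undefined variable is a plain specification error. The whole point should be fixed before analysis.

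**What to change.** 1. **Last window.** Classify every visit due on or before the earlier of endline and day 270 using all records through `latest_mre`, including visits after endline. Where records do not reach 28 (90) days past that point, censor attenders and non-attenders alike at `latest_mre` minus 28 (90) days and report retention only to that day. For example, if records stop at day 270, the 28-day curve ends at day 242.
2. **First interval.** Define `v1` as the enrolment visit (or the last prior one), so that its next-visit date starts the chain and the first return is tested. Where a located record extends more than 28 (90) days past that date with no attendance, code a loss at that date. Keep missing status only for charts not located or without usable dates, report their number by arm, and add a sensitivity analysis counting them as lost.
3. **Visit-2 flags.** Build `v2_ltfu_28` and `v2_ltfu_90` from `v2_days_aftersched`.
4. **Consistency.** Align the `v1` definition, the `n_visits` code, the missingness rules, the zero-time rule and the ITT statement.

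**Cost.** SAP wording and derivation code, and lower reported retention. Days 270 + 28 = 298 and 270 + 90 = 360 both fall within planned abstraction. The margin for the 90-day rule is only about 5 days under the SAP's 12-month limit, and abstraction is roughly quarterly, so some records may stop short and the truncation in item 1 would apply. The next-visit date from the enrolment visit must be in the extract; where it is not, it has to be pulled from the same chart.

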 - q027>today_bl AND latest follow-up date prior to transfer is missing
 t ltfu 90=9
- if **ltfu_90=9**
 - o ret_time_90=q028-today_b1

Missingness will be handled in the following way:

- If a follow-up date (i.e. **v7q044**) is missing (. or Jan 1 1990) and retained up to that point, retention must be assessed using the clinic visit date at which the follow-up date is missing. Consider retention time to be the visit date + 28 days as a conservative estimate of the follow-up time. Consider censored if retained up to that point.
- If a participant has died [died==1] but is missing date of death [q028] and appears to be retained throughout the entire study period, retention time is assessed based on the latest attended visit (i.e. v2q036), given that we do not know if participant died prior to the scheduled follow-up date.
- If a participant has transferred [transfer==1] but is missing date of transfer [q027] and appears to be retained throughout the entire study period, participant is categorized as transferred (ltfu_28/ltfu_60/ltfu_90==8) and retention time is assessed based on the latest available follow-up date (i.e. v7q044)
- If medical record data are incomplete towards the end of the study period (i.e. **latest_mre** falls before **today_el/today_el_approx**), then retention is assessed using **latest_mre** as the pseudo-endline date. Retention cannot be assessed into the future.
- If no visit data for participant during the study period or all visit dates for participant are missing during the study period (. or jan 1 1990), then retention time is missing and LTFU status is missing.
- We will generate a variable, conservative, to indicate whether participants have complete medical record data (conservative=1) or have a gap during the beginning of the study period conservative=.).

conservative=1 if (v1q036-today_bl)<=56 & v1q036!=.

conservative=. otherwise

Other variables for descriptive analysis of retention data

Other variables will be created to describe retention and clinic visits during the study period:

n_visits=number of clinic visits attended during the study period

• Code:gen n_visits=.

```
forvalues i=11(-1)1 {
replace n_visits=`i' if v`i'q036!=. & n_visits==. & ((v`i'q036<=today_el &
today_el!=.) | (v`i'q036<today_el_approx & today_el_approx!=.))
}
replace n visits=0 if v1q036==. | ( v1q036<today bl & v2q036==.)</pre>
```

n missed 28=Number of clinic visits missed by more than 28 days during the study period

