failvar - failure variable, created ordinal variable ltfu 28 defined above
```

The origin command includes participants with 0 survival time because these participants had the potential to be retained in care during the study period. The exit command specifies that 270 days is the latest timepoint at which we will assess retention.

Kaplan-Meier cumulative retention probabilities at endline with 95% confidence intervals, by study group:

sts list, by(group_itt) ci

Plots by study group:

sts graph, by(group_itt) ci

Log-rank test for difference in retention between groups , stratified by site:

sts test group, strata(facility) detail

Secondarily, we will also conduct the survival analysis described above using the 90 day cutoff variables (i.e. ltfu_90, ret_time_90).

We will also report on the proportion of participants, by study arm, who are retained at 12 months after enrollment. We will use additional regression models (For example, a multivariate Cox proportional hazards model) to explore factors associated with retention in further detail, such as time on ART at enrollment, age, and sex.

If the variables other than retention included in these models have ≥5% missingness, a multiple imputation model will be run as a secondary analysis. Multiple imputation creates multiple sets of plausible values for missing data that reflect the uncertainty about the missing data. The imputation model will include additional variables that are theoretically related to the variables being imputed (Chantala & Suchindra; Stuart, 2009; White, 2011): Age, sex, date of HIV test, date of ART initiation, depression, and social support. We will impute individual items (for example, individual items missing from the social support measure), rather than generated scores. Although there is some controversy as to whether to round categorical variables after imputation (Allison, 2005), we will round the values in each variable in order to facilitate interpretation of results and given expected very small proportion of missing data.

The multiple imputation procedure involves 3 phases (Rubin, 1996; Yuan, 2000):

- 1. The missing data are filled in m times to generate m complete data sets.
- 2. The m complete data sets are analyzed by using standard procedures.

3. The results from the m complete data sets are combined for inference.

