Two main assumptions underlie the multiple imputation procedure. First, the data are assumed to be missing at random (MAR). According the SAS User Guide (2003a), for a variable to be MAR, "the probability that an observation is missing can depend on the observed variable values of the individual, but not on the missing variable values of the individual." Although the MAR assumption cannot be verified, since independence from the missing values cannot be estimated, Schafer states that the assumption becomes more plausible as the number of variables included in the imputation model increases (Schafer, 1997). We will assess MAR and verify that there is no reason to think the missing-at-random assumption is violated using the mi misstable patterns command specified for the variables to be included in the multiple imputation. The second assumption is that of multivariate normality. However, according to Schafer (1997), inferences based on multiple imputation can be robust to departures from the assumption if the amount of missing data is not large.

The mi set of commands (mi set, mi impute, and mi estimate) will be used for the multiple imputation procedure. To allow results to be reproducible, a random-number seed will be set. M=10 imputed datasets will be created.

For participants that have complete medical record for the study period (i.e. conservative=1, ltfu 28!=. and ret time 28!=0), we will also descriptively present the following by ITT intervention arm:

- n visits=number of clinic visits attended during the study period
- n missed 28=Number of clinic visits missed by more than 28 days during the study period •
- mean followup mo=Mean months of follow-up time during the study period ٠

Objective 2.

To examine the association between treatment exposure and secondary outcomes of social support, HIV knowledge and treatment literacy, adherence and viral suppression, we will conduct significance testing using two-sided tests, with an alpha of 0.05. To examine the relationship between treatment exposure and social support, a continuous variable, we will conduct a t-test using treatment exposure (group) and change from baseline to endline in social support score (ss avg chng). We will similarly examine the relationship between treatment exposure and HIV knowledge by conducting a t-test using treatment exposure (group) and change from baseline to endline in total knowledge score (know chng).

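### The by-arm table of clinic visits selects on early attendance after randomisation, not on completeness of the abstracted record

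*SAP*

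**What the plan says.** **The flag (SAP IV.C, missingness rules under retention for survival analysis).** A variable is created "to indicate whether participants have complete medical record data (conservative=1) or have a gap during the beginning of the study period". The code is "conservative=1 if (v1q036-today_bl)<=56 & v1q036", followed by a check that the date is not the Stata missing value. All others get a missing flag. The same section states that "v1 denotes the first attended visit after study enrollment".

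**The no-visit rule (same list).** If a participant has no usable visit date in the study period, "then retention time is missing and LTFU status is missing".

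**The table (SAP VI, Objective 1).** The restriction reads: "For participants that have complete medical record for the study period (i.e. conservative=1, ltfu 28!=. and ret time 28!=0" (the parenthesis closes there). For that group, "we will also descriptively present the following by ITT intervention arm", and the three visit measures are listed.

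**The survival analysis (same objective).** The origin setting "includes participants with 0 survival time because these participants had the potential to be retained in care during the study period".

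**The purpose (Protocol, Analyses, Primary Objective).** Beyond the log-rank comparison, retention is to be described in terms of lapses in care and returns to treatment over follow-up.

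**The concern.** The label and the rule describe different things. A record is complete if the clinic file was found and abstracted to the end of the period. The SAP has a variable for how far abstraction reached, `latest_mre`, but the flag does not use it. It looks only at when the participant first came back, which happens after randomisation and is part of the outcome. A fully abstracted participant first seen on day 60 is classed as having a gap, while one whose abstraction stopped early can pass.

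The other two conditions act in the same direction. Participants with no visit data are removed because their LTFU status is missing. Zero-time participants are removed here although the survival analysis keeps them for a stated reason.

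The table is meant to describe attendance by arm. If the intervention prevents early loss, the arms lose different shares to the filter, and part of the difference the table should show is taken out before it is drawn up. The SAP does not ask for the number excluded per arm, so a reader could not see this.

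**Working it through.** **1. What the flag does, case by case**

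| First recorded visit `v1` | Flag | Comment |
|---|---|---|
| missing | excluded | includes a participant with an abstracted file who never returned |
| day 28 or day 56 | kept | |
| day 57 | excluded | a late return is read as a record gap |
| day 84 | excluded | on time if the scheduled interval was about three months |
| before baseline | kept | conflicts with the SAP's own definition of `v1` |
| 1 Jan 1990 (a missing-date code in the SAP) | kept, unless recoded first | only the Stata missing value is tested |

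Visits are typically monthly (Protocol, Sampling procedure and recruitment). With a 28-day interval and the 28-day grace period, 28 + 28 = 56. Failing the flag is then the same as being more than 28 days late for the first visit.

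**2. How the conditions fit the rest of the SAP**

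- `n_visits` is set to 0 when `v1q036` is missing, but those participants fail the flag, so that zero never reaches the table.
- The other zero branch (`v1` before baseline, no `v2`) passes the flag. Under the no-visit rule its LTFU status appears to be missing, so it would be dropped as well.
- Relaxing the flag alone would not bring never-returners back, because the LTFU-status condition also removes them.

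**3. The planning rates used for size**

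The SAP's sample size is not in dispute; it supplies the rates. With 12-month retention p = 0.45 (control) and 0.575 (intervention), HR = ln 0.575 / ln 0.45 = 0.693. Schoenfeld's formula gives 4 × (1.960 + 0.842)² / (ln 0.693)² = 233.5, so 234 events. With exponential event times and 10% exponential loss, the event probabilities are 0.526 and 0.405, mean 0.4655. Then 234 / 0.4655 gives N = 503, against the stated 500. The rates reproduce.

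**4. Illustration of the effect on mean visits**

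Assumptions: visits every 28 days, nine of them by day 270; exponential loss; no one who lapses returns; no incomplete abstraction; never-returners counted as 0 visits. Let f be the share of losses who never come back. The documents do not give f for this trial. It is varied from 0 to 1430/2939 = 48.7%, the figure in the Protocol's Background for patients aged 15–21 starting ART.

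- Share not lost at once: k = 1 − f(1 − p)
- Chance of attending each next visit: q = (p/k)^(28/365)
- Mean visits, all randomised: k × (q + q² + … + q⁹)
- Mean visits, filtered table: (q + q² + … + q⁹) / q
- Removed, of 250: 250 × (1 − kq)

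| f | Removed, control / intervention | All randomised: control, intervention, difference | Filtered: control, intervention, difference |
|---|---|---|---|
| 0 | 15 / 10 | 6.71, 7.32, **0.61** | 7.13, 7.64, **0.51** |
| 25% | 45 / 34 | 6.10, 6.82, **0.72** | 7.43, 7.89, **0.46** |
| 48.7% | 74 / 57 | 5.49, 6.32, **0.83** | 7.79, 8.17, **0.38** |

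For the last control row: k = 1 − 0.4866 × 0.55 = 0.7324; p/k = 0.6144; q = 0.9633; 250 × (1 − 0.7324 × 0.9633) = 74. In every row more controls are removed, both means rise and the difference narrows.

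**The case against.** **The table is descriptive, and ITT only names the grouping.** This stands. A reader might infer that the trial's intention-to-treat analysis is compromised. The documents do not support that. The ITT sentence in SAP IV covers primary analyses, the table carries no test, and the Kaplan-Meier and log-rank commands use neither the flag nor this filter. How the missing-status rule bears on the survival data is a separate question, not assessed here.

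**The flag may detect real gaps.** Participants are recruited at clinic visits, and the `n_visits` code allows for a `v1` before baseline. If `v1` can be the enrolment visit, a first recorded visit more than 56 days later does suggest a gap, and a never-returner could pass the flag. This stands as a reason to reconcile the text. It does not rescue the rule, because the SAP defines `v1` as following enrolment, and on that definition the flag measures return to clinic.

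**Never-returners are dropped by another condition.** Correct. The removal cannot be blamed on the 56-day flag alone. What the flag adds is mainly those first seen on day 57 or later, whom the illustration does not model. The point concerns the three conditions together.

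**The benefit would not vanish.** A reader might infer that early benefit disappears from the table entirely. That follows only if everyone kept is assumed to have the same number of visits in both arms. Later losses also differ by arm, and a difference remains in every row above.

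**Showing all participants breaks two measures.** Also correct. Mean follow-up divides by `n_visits`, so it is undefined at zero. The row total behind `n_missed_28` gives 0 missed visits to someone who never returned. The fix has to deal with both.

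**The 1 Jan 1990 code may be cleaned beforehand.** Possibly: the SAP treats it as missing elsewhere. The recode should be stated, since the flag and `n_visits` code do not screen it.

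**Conclusion.** The concern holds for this descriptive table. As written, a by-arm description of visit behaviour is conditioned on early attendance after randomisation, under a label that says record completeness. The primary log-rank comparison does not use the filter.

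At the planned rates, the illustrative difference in mean visits narrows by 0.10 with no extra early loss (0.61 to 0.51) and by 0.45 if 48.7% of losses never return (0.83 to 0.38). The direction relies on the intervention reducing loss as planned. The upper figure relies on a share from patients starting ART at ages 15–21. This trial enrols ages 15–24 with up to 12 months on ART, so its share may well be lower. If `v1` can be the enrolment visit, fewer participants are removed. The mislabelling and the unreported exclusions do not depend on these assumptions.

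**What to change.** In SAP IV.C:

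- State one definition of `v1`, make the code agree with it, and count only visits after `today_bl`.
- Recode 1 Jan 1990 to missing before the flag and the `n_visits` code run.
- Define record completeness from abstraction: record abstracted, and `latest_mre` on or after the endline date. Do not use attendance.

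In SAP VI, Objective 1:

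- Present `n_visits` for all randomised participants with an abstracted record, with 0 for those with no visit after baseline. Do not exclude on missing LTFU status or zero retention time.
- For `n_missed_28`, count a first scheduled visit not attended within 28 days as missed. Where no interval can be assessed, set the measure to missing, not 0.
- Present `mean_followup_mo` only among those with at least one visit, and state the denominator.
- Report the number excluded per arm. Keep the filtered table as secondary if it is wanted.

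The cost is a paragraph of SAP text and a few lines of code. No new data and no change to the primary analysis are needed.
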